1.3.2. Clinical studies of the test drug

Not performed.

1.4. Summary of known and potential risks and benefits for clinical trial subjects (risk/benefit ratio)

Benefit evaluation

BCD-089 is an innovative drug, which has never been used in humans. The first stage of BCD-089 clinical development will be to evaluate its effects in healthy volunteers, which means that participants in such a study will not derive subjective (personal) benefits from their participation in it, except for a detailed medical examination; however, data obtained after the completion of this study will have high scientific value and may help introduce into clinical practice a new highly effective product for the treatment of severe autoimmune disorders.

Risk evaluation

[REDACTED]

Translated from Russian to English, dated 06-Jul-2020

[Redacted content]

Translated from Russian to English, dated 06-Jul-2020

[Redacted content]

Translated from Russian to English, dated 06-Jul-2020

1.5. Description and justification of the study design, the method of administration of the test drug, dose, dosing regimen and the course of treatment

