1.2. Exclusion criteria

1. A history of use of monoclonal antibody products against interleukin-6 or its receptor;
2. Allergy history (anaphylactic shock or multidrug allergy);
3. Known allergy or intolerance to monoclonal antibody drugs (murine, chimeric, humanized, or human) or any other components of the study drug.
4. Major surgery less than within 30 days prior to signing the informed consent form;
5. Severe infections (including those that required hospitalization or parenteral antimicrobial/antimycotic/antiviral/antiprotozoal treatment) within 6 months before signing the ICF;
6. Systemic antimicrobial/antimycotic/antiviral/antiprotozoal treatments within 2 months before signing the ICF;
7. More than 4 episodes of respiratory infections within 6 months before signing the informed consent form;
8. Impossibility to insert a venous catheter for blood sampling (for example, due to skin diseases at venipuncture sites);
9. Diseases or other conditions that can affect the pharmacokinetics of the test product (e.g., chronic liver, kidney, blood, cardiovascular, bronchopulmonary and neuroendocrine systems disorders (including diabetes mellitus) etc.);
10. A history of fever above 40°C;
11. A history of episodes of elevated hepatic transaminases above 2.5 x ULN;
12. Epileptic seizures, history of seizures;
13. Current depression or a history of depression, suicidal thoughts/attempts at the time of the screening examination or a history of such behavior;
14. Regular use of any oral or parenteral medications, including over-the-counter drugs, vitamins, and dietary supplements within less than 2 weeks before signing the informed consent;
15. Use of medications, including OTC drugs that have a pronounced effect on hemodynamics, liver function, etc. (barbiturates, omeprazole, cimetidine, etc.) within less than 30 days before signing the informed consent form;
16. Use of medicinal products that affect the immune status (cytokines and their inducers, glucocorticoid hormones, etc.) within less than 2 months prior to signing the informed consent form;

Translated from Russian to English, dated 06-Jul-2020

17. Vaccination within 4 weeks prior to signing of informed consent form;
18. Values of standard laboratory tests and investigations results that are beyond the reference ranges;
19. Smoking more than 10 cigarettes per day;

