20. Consumption of more than 10 units of alcohol per week (1 unit of alcohol is equivalent to ½ liter of beer, 200 mL of wine or 50 mL of liquor) or a history of alcoholism, drug addiction or drug abuse;
21. Donation of 450 mL or more of blood or plasma within 2 months prior to signing of the informed consent form;
22. Participation in other clinical studies within less than 2 months before signing the informed consent form or simultaneous participation in other clinical studies;
23. Prior participation in this clinical study.

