9. STATISTICAL METHODS

9.1 Calculation of the parameters of pharmacokinetics and pharmacodynamics

9.1.1. Pharmacokinetic parameters

Based on the calculated concentration values for the anti-IL-6 monoclonal antibody in the blood of each volunteer, the following pharmacokinetic variables will be estimated at time points specified in this protocol:

1. C_{\max} - maximum serum concentration of anti-IL-6 receptor antibody over the observation period.
2. t_{\max} - time to achieve maximum serum concentration (C_{\max}) of anti-IL-6 receptor antibody.
3. AUC_{0-1680} — the area under the concentration of anti-IL-6 receptor monoclonal antibody-time curve over the time interval from 0 to 1680 hours. AUC_{0-1680} will be calculated using the trapezoid method using the following formula, where C_p is the concentration of the drug BCD-089 in the blood at the time t_p in hours:

$$t_p \in \{0; 2; 8; 12; 24; 48; 72; 96; 120; 168; 240; 336; 504; 672; 1176; 1680\}_{p=1, \dots, 16}$$

4. $AUMC_{0-1680}$ - total area under the curve of the concentration of anti-IL-6 receptor monoclonal antibody multiplied by time over the time interval from 0 to 1680 hours. $AUMC_{0-1680}$ will be calculated using the following formula:

$$AUMC_{0-1680} = \sum_{p=2}^{16} \frac{(C_p * t_p + C_{p-1} * t_{p-1}) * (t_p - t_{p-1})}{2},$$

where C_p — concentration of anti – IL – 6

– receptor monoclonal antibody против рецептора ИЛ6

Translated from Russian to English, dated 06-Jul-2020

in the blood at t_p

$$t_p \in \{0; 2; 8; 12; 24; 48; 72; 96; 120; 168; 240; 336; 504; 672; 1176; 1680\}_{p=1, \dots, 16}$$

5. **Total clearance (Cl)** is a parameter that reflects the volume of test tissue, which is cleared from the anti-IL-6 receptor monoclonal antibody per unit of time and is determined by the ratio of the anti-IL-6 receptor monoclonal antibody dose (*DOSE*) to $AUC_{(0-1680)}$:

$$CL = \frac{DOSE}{AUC_{0-1680}}$$

6. **Mean residence time (MRT)** of the anti-IL-6 receptor monoclonal antibody molecule in the body will be calculated as the ratio of $AUMC_{0-1680}$ to AUC_{0-1680} :

$$MRT = \frac{AUMC_{0-1680}}{AUC_{0-1680}}$$

7. **Elimination constant** of the anti-IL-6 receptor monoclonal antibody (k_{el}) will be determined using the following formula:

$$k_{el} = \frac{1}{MRT}$$

8. **Half-life period** of the anti-IL-6 receptor monoclonal antibody ($T_{1/2}$) will be determined using the following formula:

$$T_{1/2} = \frac{\ln(2)}{k_{el}} = \ln(2) * MRT$$

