9.7 Patient selection for analysis

Demographic data and baseline clinical and laboratory characteristics will be evaluated in all volunteers included in the study.

Safety analysis

Safety analysis will include all volunteers who received the test drug.

Pharmacokinetic analysis

Pharmacokinetics analysis will include data from volunteers who have received BCD-089 and have had no more than two missing/lost/damaged blood serum samples for pharmacokinetics and had no more than two consecutive missing/lost/damaged samples and for whom a serum sample obtained before the test drug administration is available for the analysis.

Pharmacodynamic analysis

Pharmacodynamics analysis will include data from volunteers who have received BCD-089 and have had no more than two missing/lost/damaged of whole blood and/or blood serum for pharmacodynamics studies, and for whom a serum sample obtained before the test drug administration is available for the analysis.

Immunogenicity analysis

Immunogenicity analysis will include data from volunteers who have received BCD-089 and have not had missing/lost/damaged serum samples taken on Days 1 and 71 of the study.

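### The PK analysis set requires a pre-dose serum sample although the true pre-dose BCD-089 concentration is zero by design, so one unavailable sample can remove a complete post-dose curve from a cohort of three or one

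*Combined protocol and SAP*

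**What the plan says.** Section 9.7 (Patient selection for analysis), repeated in the synopsis, defines the PK set by three conditions beyond having been dosed. Volunteers must "have had no more than two missing/lost/damaged blood serum samples for pharmacokinetics". The second and third conditions follow in one clause, which limits the set to volunteers who "had no more than two consecutive missing/lost/damaged samples and for whom a serum sample obtained before the test drug administration is available". The third condition, on the pre-dose sample, carries no exception. The PD set has the same pre-dose condition, and the immunogenicity set requires the Day 1 and Day 71 samples.

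Other parts of the protocol bear on it:

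- Section 1.4 describes the product: "BCD-089 is an innovative drug, which has never been used in humans". Section 1.2.1 specifies a single subcutaneous dose.
- The exclusion criteria in section 5 (printed as 1.2) bar "A history of use of monoclonal antibody products against interleukin-6 or its receptor" (item 1) and "Prior participation in this clinical study" (item 23).
- Section 9.1.1 gives the PK grid in hours: "0; 2; 8; 12; 24; 48; 72; 96; 120; 168; 240; 336; 504; 672; 1176; 1680".
- Section 7.1 names AUC0-1680 and AUC0-∞ as the primary PK parameters.
- Section 11.2 lists two or more missing PK/PD samples among examples of probable major deviations, and requires a volunteer with a major deviation to be left out of the final PK/PD analysis.
- Section 9.5, on missing and non-evaluable data, and section 4.6.3.6.1, on the BCD-089 assay, are redacted.

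**The concern.** For PD the pre-dose condition is sound. Baseline CRP, IL-6 and soluble receptor are unknown until measured, and change cannot be read without them. For PK the quantity at time 0 is the concentration of a drug that no volunteer has yet received. Its true value is known without a sample.

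The condition therefore excludes a volunteer from the primary PK analysis for lack of a number that could be written in, while tolerating the loss of a sample that cannot be. At stake is a full concentration-time curve in a design with three mandatory volunteers per dose, and one at the lowest dose.

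**Working it through.** **1. The plan's own count.** Cohort 01 has 1 volunteer. Cohorts 02 to 07 have 3 mandatory volunteers each, plus 3 more if a DLT occurs.
- Maximum: 1 + 6 × (3 + 3) = 37, which matches the synopsis.
- Mandatory: 1 + 6 × 3 = 19.

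**2. Samples.** The grid has 16 times: one at time 0 and 15 after dosing.

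**3. True value at time 0.** There has been no earlier human exposure, each volunteer is dosed once, and re-enrolment is barred. The true BCD-089 concentration before dosing is therefore zero. The bar on earlier anti-IL-6 and anti-IL-6R antibodies also removes an obvious source of interference.

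**4. Weight of time 0 in each parameter (linear trapezoid, section 9.1).**
- AUC0-1680: C(0) enters only the 0-2 h interval, with coefficient (2 − 0)/2 = 1 h. As a time weight this is 1/1680 = 0.06%; it is not a share of AUC. If the assay would have read a background value b, substituting zero changes AUC0-1680 by b × 1 h.
- AUMC0-1680: C(0) is multiplied by t = 0 and contributes nothing.
- CL = dose/AUC, MRT = AUMC/AUC, kel = 1/MRT and T1/2 = ln(2) × MRT move only through that same 1 h term.
- AUC0-∞ = AUC0-1680 + C(1680)/kel uses time 0 only through AUC0-1680 and kel.
- Cmax and Tmax are the highest measured value and its time, so a zero at time 0 does not affect them.
- Section 7.1 specifies the logarithmic trapezoid instead. That formula cannot be evaluated with a zero endpoint, whether the zero is measured or substituted, so the choice of method does not favour requiring the sample.

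**5. Comparison with the last sample.** C(1680) has coefficient (1680 − 1176)/2 = 252 h in AUC0-1680, against 1 h for C(0). The interval it closes is 504/1680 = 30% of the window, and it also enters AUC0-∞ directly.

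| Volunteer | Section 9.7 | Section 11.2 (two or more missing) |
|---|---|---|
| Lacks only the 1680 h sample | meets all three conditions | below threshold |
| Lacks only the pre-dose sample | fails the third condition | below threshold |

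On these rules the first volunteer stays in the PK set and the second is excluded.

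**6. Cost to a cohort.** The loss is 1 of 3 volunteers (33%) in cohorts 02 to 07 without a DLT, and 1 of 1 in cohort 01. Replacement is not clearly available. Section 5.3.1 allows it for withdrawals unrelated to the drug and for non-compliance, and section 6.6 sets the missed-sample criterion at more than two.

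**7. How often.** The documents give no loss rate. Assume each volunteer independently has probability p of lacking any qualifying pre-dose sample.

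| Assumed p | Three-person cohort, 1 − (1 − p)^3 | All 19 mandatory volunteers, 1 − (1 − p)^19 |
|---|---|---|
| 1% | 3.0% | 17% |
| 2% | 5.9% | 32% |
| 5% | 14.3% | 62% |

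**The case against.** The best argument for the condition is that a true zero does not guarantee an assay reading of zero. Section 1.1 says the soluble target receptor is present in all body fluids, and the assay description is redacted. A pre-dose reading is the only individual check on background, so a reader who infers that the sample carries no PK information goes too far. This stands as a reason to collect and assay the sample. It does not show that a volunteer without it should lose the other 15 points.

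Three further objections limit the point:

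- The third condition says a serum sample, not a PK serum sample. The PD grid also starts at time 0, so another pre-dose tube might satisfy it. Tube and aliquot details are redacted, so it is not established that losing one particular tube triggers exclusion. The redacted section 9.5 might also contain a handling rule, but the condition in 9.7 is unconditional as printed.
- A reader might infer from 9.7 that a volunteer who lacks two informative post-dose samples is kept while one who lacks only the pre-dose sample is dropped. Section 11.2 does not support this, because it treats two missing samples as a probable major deviation leading to PK/PD exclusion. The contrast holds for one missing sample, such as 1680 h.
- A reader might put the cost as a confidence interval 3.6 times wider (95% t half-width 2.48 SD at n = 3, 8.98 SD at n = 2). The statistical methods section lists descriptive summaries and rank tests, with no such interval for a cohort mean, so that ratio is not a consequence for any listed analysis.

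The event is also uncommon in any one cohort. The pre-dose draw takes place on site on the dosing morning, so the main risk is damage or loss afterwards. The volunteer remains in the safety set, and section 9.6 allows a change of plan to be explained in an amendment or report.

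**Conclusion.** The point holds as a minor refinement. As printed, the PK set can exclude a complete 15-point post-dose curve for want of a value whose true level is fixed at zero by the design and whose weight in AUC0-1680 is 1 h of 1680 h. Each occurrence costs a third of a three-person cohort's PK data, or all PK data at 0.06 mg/kg.

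The 17% to 62% range across 19 volunteers rests entirely on the assumed 1% to 5% loss rate, on independence, and on no other pre-dose tube meeting the condition. The conclusion also assumes that the redacted missing-data section does not already override 9.7. It does not extend to the PD or immunogenicity sets.

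Separately, sections 9.7 and 11.2 disagree about a volunteer with exactly two missing PK samples: the first tolerates two, while the second lists two or more as a probable ground for exclusion.

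**What to change.** In section 9.7 and the synopsis:

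- Remove the pre-dose condition from the PK set only, and state that C(0) is set to 0 when the pre-dose sample is unavailable.
- Continue to collect and assay the pre-dose PK sample. List any measurable pre-dose value and report the PK results with and without that volunteer.
- Keep the pre-dose condition for the PD set and the Day 1 sample for immunogenicity.
- Reconcile the missing-sample limits of 9.7 and 11.2, and state that a missing pre-dose PK sample counts towards neither.

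The cost is a sentence or two in 9.7 and the synopsis and one aligned line in 11.2, with no change to dosing, visits or sampling. The downside is that assay background cannot be checked individually for a volunteer without a pre-dose sample. It remains documented in the other volunteers.

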	
 ✓ AUC_{0-1680} (area under the concentration-time curve from the administration of the drug to 1680 h (71 days after administration) and $AUC_{0-\infty}$ (to infinity). 
Secondary:
 
 ✓ C_{min} (minimum detectable concentration in blood serum), ✓ T_{min} (time to minimum serum concentration). 
2. Determination of IL-6 concentration:
 
Primary:
 
 ✓ AUC_{0-1680} (area under the concentration-time curve from the administration of the drug to 1680 h (71 days after administration) and $AUC_{0-\infty}$ (to infinity). 
Secondary:
 
 ✓ C_{max} (maximum concentration in serum), ✓ T_{max} (time to maximum serum concentration). 
3. Determination of soluble IL-6 receptor concentration:
 
Primary:
 
 ✓ AUC_{0-1680} (area under the concentration-time curve from the administration of the drug to 1680 h (71 days after administration) and $AUC_{0-\infty}$ (to infinity). 
Secondary:
 
 ✓ C_{max} (maximum concentration in serum), ✓ T_{max} (time to maximum serum concentration). 
It will be additionally calculated within the study of pharmacodynamics based on the results of flow cytometry:
 
 ✓ Percentage of occupancy of membrane IL-6 receptors with BCD-089 2 hours after drug administration, 168, 336 and 504 hours after single injection¹
Pain assessment endpoint	
 ✓ The mean pain score during the injection on the visual analogue scale.
Safety endpoints:	
 ✓ Proportion of subjects who developed SAEs in each cohort. ✓ Proportion of subjects who developed AEs in each cohort.

¹ Given parameter is not an endpoint in the study.

Translated from Russian to English, dated 06-Jul-2020

	
 ✓ Proportion of subjects who developed local reactions in each cohort. ✓ Proportion of subjects who developed grade 3-4 AEs and SAE in each cohort. ✓ Proportion of subjects who developed any grade neutropenia in each cohort. ✓ Proportion of subjects who discontinued the study due to AEs and SAEs in each cohort. 																																

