4.1.2. Pharmacodynamic endpoints

1. **C-reactive protein concentration determination:**

Translated from Russian to English, dated 06-Jul-2020

Primary:

- AUC_{0-1680} (area under the concentration-time curve from the administration of the drug to 1680 h (71 days after administration) and $AUC_{0-\infty}$ (to infinity).

Secondary:

- C_{min} (minimum detectable concentration in blood serum),
- T_{min} (time to minimum serum concentration).

2. **Determination of IL-6 concentration, soluble IL-6 receptor concentration:**

Primary:

- AUC_{0-1680} (area under the concentration-time curve from the administration of the drug to 1680 h (71 days after administration) and $AUC_{0-\infty}$ (to infinity).

Secondary:

- C_{max} (maximum concentration in serum),
- T_{max} (time to maximum serum concentration).

Additionally, the percentage of occupancy of membrane IL-6 receptors with BCD-089 2 hours after drug administration, 168, 336 and 504 hours after single injection will be determined in the study (however, it is not specified in the mandatory analyzed endpoints as it is a pilot study).

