Due to the need for multiple blood sampling, the volunteer has to stay at the study site for the first day after the injection.

Safety and tolerability assessment

Safety and tolerability will be assessed by monitoring vital signs (blood pressure, heart rate, and body temperature), conducting periodic physical examinations, assessing the frequency and severity of local reactions, and evaluating the results of complete blood count and blood biochemistry tests, urinalysis, and electrocardiography. These parameters will be assessed over a period of 71 days after a single-dose administration of the test drug. Additionally, information about the tenderness of subcutaneous injection, evaluated by a volunteer using a 10-point visual analog scale, will be analyzed.

Pharmacokinetic assessment

Pharmacokinetic assessment will be carried out based on data on the BCD-089 concentration in the serum of healthy volunteers. Volunteers included in the study arrive at the study site on the morning of the drug administration day. A venous catheter is installed immediately before the first blood sampling (the time from the catheter placement to the first blood sampling from it should not exceed one hour). Since multiple blood sampling is carried out only during the first day after the test drug administration, the time of placement a venous catheter will be 24 hours, after which the blood is taken by venipuncture. Detailed description of blood sampling points is presented in Table 3 below.

Translated from Russian to English, dated 06-Jul-2020

Pharmacodynamics and immunogenicity assessment

Pharmacodynamics assessment will be carried out based on data on the concentrations of C-reactive protein, soluble IL-6 receptor, human IL-6 in the serum of healthy volunteers.

Table 4. Detailed description of blood sampling for CRP, sIL-6R, IL-6 testing

Visit	Sample labeling number	Blood sampling time	Acceptable window for blood sampling	Blood volume (for 3 types of analyzed substances)
[REDACTED]	[REDACTED]	[REDACTED]	[REDACTED]	[REDACTED]
[REDACTED]	[REDACTED]	[REDACTED]	[REDACTED]	[REDACTED]
[REDACTED]	[REDACTED]	[REDACTED]	[REDACTED]	[REDACTED]
[REDACTED]	[REDACTED]	[REDACTED]	[REDACTED]	[REDACTED]
[REDACTED]	[REDACTED]	[REDACTED]	[REDACTED]	[REDACTED]
[REDACTED]	[REDACTED]	[REDACTED]	[REDACTED]	[REDACTED]
[REDACTED]	[REDACTED]	[REDACTED]	[REDACTED]	[REDACTED]
[REDACTED]	[REDACTED]	[REDACTED]	[REDACTED]	[REDACTED]
[REDACTED]	[REDACTED]	[REDACTED]	[REDACTED]	[REDACTED]

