- ✓ T_{max} (time to maximum serum concentration).

Based on the results of flow cytometry, the following parameters will be calculated (a pilot study, it is not the endpoint)

- ✓ Percentage of occupancy of IL-6 receptors with BCD-089 2 hours after drug administration, as well as in 168, 336 and 504 hours.

[REDACTED]

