9.1.2. Pharmacodynamical parameters

Based on the obtained concentrations of C-reactive protein, IL-6 and soluble IL-6 receptor in the blood of each volunteer, the following pharmacodynamic parameters will be calculated at the Protocol-specified time intervals:

1. C_{\max} – maximum blood concentration of C-reactive protein, IL-6 and soluble IL-6 receptor over the observation period.
2. t_{\max} – time to maximum blood concentration (C_{\max}) of C-reactive protein, IL-6 and soluble IL-6 receptor.
3. AUC_{0-1680} – the area under the concentration-time curve for C-reactive protein, IL-6 and soluble IL-6 receptor over the time interval from 0 to 1680 hours. AUC_{0-1680} is calculated using the trapezoidal method with the following formula:

$$AUC_{0-1680} = \sum_{p=2}^{16} \frac{(C_p + C_{p-1}) * (t_p - t_{p-1})}{2},$$

where C_p concentration of C – reactive protein, IL – 6 and soluble IL
– 6 receptor values

ИЛ6 in the blood at t moment of time t_p (hours),

$$t_p \in \{0; 2; 8; 12; 24; 48; 72; 96; 120; 168; 240; 336; 504; 672; 1176; 1680\}_{p=1, \dots, 16}$$

4. C_{\min} – minimum blood concentration of C-reactive protein, IL-6 and soluble IL-6 receptor over the observation period.
5. t_{\min} – time to minimum blood concentration (C_{\min}) of C-reactive protein, IL-6 and soluble IL-6 receptor.

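### One missing-sample limit covers both whole blood and serum in the PD analysis set, so losses in the receptor-occupancy pilot can remove a volunteer from the primary serum PD analysis

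*Combined protocol and SAP*

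**What the plan says.** Section 9.7 (Patient selection for analysis) and the synopsis give one PD analysis set in identical words. A volunteer must have been dosed, have a pre-dose serum sample, and have "no more than two missing/lost/damaged of whole blood and/or blood serum for pharmacodynamics studies". No separate set or count is given for any PD assay.

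The primary PD parameters are areas under the curve for CRP, IL-6 and soluble IL-6 receptor (Section 4.1.2: "area under the concentration-time curve from the administration of the drug to 1680 h"). Section 4.2 bases them on "data on the concentrations of C-reactive protein, soluble IL-6 receptor, human IL-6 in the serum of healthy volunteers". Section 9.1.2 lists 16 sampling times in hours: "0; 2; 8; 12; 24; 48; 72; 96; 120; 168; 240; 336; 504; 672; 1176; 1680".

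Membrane receptor occupancy is the only other PD assay visible. The synopsis places it inside pharmacodynamics ("It will be additionally calculated within the study of pharmacodynamics based on the results of flow cytometry") and adds in a footnote: "Given parameter is not an endpoint in the study". Section 4.1.2 says that "it is not specified in the mandatory analyzed endpoints as it is a pilot study". Section 7.2 names four post-dose times: "Percentage of occupancy of IL-6 receptors with BCD-089 2 hours after drug administration, as well as in 168, 336 and 504 hours".

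Three other sections bear on the same samples:
- Section 6.6 calls a volunteer non-compliant if more than two PK and PD blood samples were missed.
- Section 5.3.1 allows non-compliant volunteers to be substituted.
- Section 11.2 gives two or more missed PK/PD samples as an example of a probable major deviation, and requires volunteers with any major deviation to be left out of the final PK/PD analysis.

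**The concern.** The two kinds of sample differ in status. Serum carries the primary PD endpoints. Occupancy is exploratory and contributes nothing to the CRP, IL-6 or soluble-receptor curves. A shared limit of two lets losses in the exploratory assay decide who enters the primary analysis. It also works in reverse: usable occupancy results drop out when three serum samples are lost.

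Cohorts 02 to 07 have three volunteers each unless a dose-limiting toxicity triggers expansion to six. A volunteer with a complete serum profile who is removed for lost occupancy tubes takes a third of the PD data at that dose level with him.

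**Working it through.** **Inputs from the documents**
- Limit: two missing samples, plus a pre-dose serum sample (Section 9.7).
- Serum PD times: 16, one of them pre-dose (Section 9.1.2).
- Occupancy times: four named post-dose (Section 7.2). The redacted occupancy table in Section 4.2 shows five rows, so four and five tubes are both run.
- Cohort sizes (sample size table): minimum 1 + 6 × 3 = 19; maximum 1 + 6 × (3 + 3) = 37, which reproduces the stated planned maximum of 37.

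**Assumptions, not in the documents**
- Each serum sample is lost with probability 2%.
- Each occupancy tube is lost with probability 2% to 30%.
- Losses are independent.

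**Direct application of the rule**
- 0 of 16 serum samples and 3 occupancy tubes lost: 3 > 2, excluded, whether the limit is pooled or applied to each sample type.
- 2 serum samples and 1 occupancy tube lost: pooled count 3 > 2, excluded. With separate limits, retained.

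**Probability of exclusion**

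Let S be the losses among the 15 post-dose serum samples, S ~ Bin(15, 0.02), and W the losses among m occupancy tubes, W ~ Bin(m, p). The pre-dose sample is present with probability 0.98.

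P(S=0) = 0.7386, P(S=1) = 0.2261, P(S=2) = 0.0323; sum 0.9970.

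*Serum only:* 1 − 0.98 × P(S ≤ 2) = 1 − 0.98 × 0.9970 = **2.3%**.

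*Pooled:* 1 − 0.98 × [P(S=0)·P(W≤2) + P(S=1)·P(W≤1) + P(S=2)·P(W=0)].

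Example with m = 5 and p = 10%: P(W≤2) = 0.9914, P(W≤1) = 0.9185, P(W=0) = 0.5905. The bracket is 0.7322 + 0.2077 + 0.0191 = 0.9590, and 1 − 0.98 × 0.9590 = 6.0%.

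*Separate limits of two per sample type:* 1 − 0.98 × P(S ≤ 2) × P(W ≤ 2).

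| Tube loss p | Serum only | Pooled (4–5 tubes) | Separate limits (4–5 tubes) |
|---|---|---|---|
| 2% | 2.3% | 2.6–2.7% | 2.3% |
| 5% | 2.3% | 3.2–3.6% | 2.3–2.4% |
| 10% | 2.3% | 4.8–6.0% | 2.7–3.1% |
| 20% | 2.3% | 10.1–14.4% | 5.0–8.0% |
| 30% | 2.3% | 18.5–27.2% | 10.5–18.2% |

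Over the 18 mandatory volunteers in cohorts 02 to 07, the expected number excluded is 18 × 0.0230 = 0.41 on serum alone. Pooled, it is 0.47–0.48 at 2% tube loss (18 × 0.0260 to 18 × 0.0269) and 0.87–1.08 at 10% (18 × 0.0481 to 18 × 0.0602). One exclusion is 1/3 = 33% of an unexpanded cohort.

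At 10% tube loss, three or more lost tubes in one volunteer has probability only 0.4–0.9%. Most of the pooled increase there comes from mixed serum and tube losses.

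**The case against.** **The link from whole blood to occupancy is not stated in visible text.** The occupancy method (Section 4.6.3.8) and the sampling tables in Section 4.2 are redacted. The wording might instead cover loss of one PD sample before or after processing to serum, or the and/or might mean that each analysis counts only its own samples. Section 9.5 on missing data is also redacted and could hold a rule by assay. This stands as a limit on certainty. It does not remove the point: every other visible PD assay is on serum, and neither place that defines the set states an assay-by-assay count.

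**The effect is small at ordinary loss rates.** This stands. With 2% loss for both sample types, pooling adds 0.3–0.4 percentage points. Nothing in the documents supports 10–30% tube loss. A reader who applied only the limit of two to 16 serum samples would get P(more than 2 of 16 lost at 2%) = 0.4% and infer a far larger relative effect. That baseline leaves out the pre-dose serum requirement; with it, the baseline is 2.3%.

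**A flow-cytometry failure would not plainly empty a cohort.** A reader might infer that an assay failure at three visits excludes every volunteer in the cohort. Section 9.7 counts missing, lost or damaged samples, and a failed run on an intact tube is not clearly any of these.

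**Some exclusions can be made good.** Sections 6.6 and 5.3.1 permit substitution of volunteers who missed more than two samples. This stands in part: substitution is optional and covers missed sampling rather than laboratory loss.

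**No power calculation rests on PD.** True: sample size follows from the 3+3 design. That lowers the stakes, but does not justify discarding complete primary PD profiles.

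**Conclusion.** The point holds as a drafting defect in the definition of the PD set. Taken literally, the rule lets losses in a non-endpoint pilot assay remove a volunteer with complete serum data from the primary PD analysis. This rests on whole blood being the occupancy sample, inferred by elimination, and on the redacted Section 9.5 not overriding Section 9.7.

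The size depends on assumed loss rates. Against 2.3% on serum alone, pooled exclusion is 2.6–2.7% at equal 2% loss, 4.8–6.0% at 10% tube loss and 10–14% at 20%. The documents do not support a claim that the effect is large. The correction is worth making because a single exclusion costs a third of an unexpanded cohort and the change costs almost nothing.

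Editing Section 9.7 and the synopsis alone would not be enough. Under Section 11.2, two missed occupancy samples could already count as a major deviation and remove the volunteer from both the PK and the PD analysis. That threshold also disagrees with Section 9.7, which tolerates two.

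**What to change.** In Section 9.7 and the synopsis:
- Define the serum PD set as dosed volunteers with a pre-dose serum sample and no more than two missing serum PD samples.
- Give receptor occupancy its own descriptive set, by available time point.
- State that losses in one set do not affect membership of the other.

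In the same edit, reconcile Section 11.2 (two or more missed samples) and Section 6.6 (more than two) with Section 9.7, so that missed occupancy samples do not remove a volunteer from the serum PD or PK analysis. Check that the redacted Section 9.5 agrees.

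The cost is a few sentences across four places, with no new data. It should be settled before any data are analysed.
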